7.4.1 Sensitivity Analyses of the Secondary Efficacy Endpoints

Sensitivity analyses of the secondary endpoints include:

- The analyses described in Section 7.4 for the secondary efficacy endpoints will be repeated for the PP and mITT populations.

7.5 Additional Analysis

The wound healing data from wounds that are not from primary wound pair will be listed .

The change in patient reported outcomes such as Heath (EQ-5D-5L) and Skin Index (Skindex-29) before and after end of treatment will be summarized.

8 Safety and Tolerability

All safety analyses will be conducted in the Safety population. Safety measures include adverse events, physical examinations, vital signs, and clinical laboratory tests.

8.1 Adverse Events

Verbatim descriptions of AEs will be coded using MedDRA system organ class, version to be delineated in the CSR. Summary tables will be provided for all treatment-emergent adverse events (TEAEs), but all AEs will be provided in a listing. A treatment-emergent AE is defined as any AE that newly appeared, increased

in frequency, or worsened in severity on or after the initiation of active treatment. An AE is considered treatment emergent if the AE start date and time is on or after the start date and time of the first administration treatment dose. If time of the AE is missing and it occurred on the same date as the first administration treatment dose, the AE will be defined as treatment emergent. If the start date of the AE is partial or missing and it cannot be determined if the AE occurred prior to or after the first administration treatment dose, the AE should be defined as treatment emergent.

An overall summary of AEs will include the number of subjects who experienced at least one AE of the following categories: any AE, any TEAE, any drug-related TEAE, any severe TEAE, any serious TEAE, any drug-related SAE, any serious TEAE leading to death, any TEAE leading to premature discontinuation of treatment, any TEAE leading to premature discontinuation from the study, any TEAE leading to dose interruption of treatment, and any serious TEAE leading to premature discontinuation of treatment dose.

The number and percentage of subjects reporting a TEAE will be tabulated by system organ class and preferred term; by system organ class, preferred term, and severity (mild, moderate, and severe); and by system organ class, preferred term, and relationship (unrelated or related to treatment). The incidence of TEAEs will be summarized by preferred term, sorted by decreasing frequency in the B-VEC group, for all TEAEs, related TEAEs, serious TEAEs, and TEAEs leading to study drug discontinuation. The number and percentage of subjects reporting a TEAE of wound site reaction (based on the MedDRA higher level term) will be tabulated, preferred term and severity (mild, moderate, and severe). The incidence of serious TEAEs, TEAEs leading to premature discontinuation of treatment dose, and TEAEs leading to a dose interruption of treatment dose will be summarized by system organ class and preferred term. For all analyses of TEAEs, if the same AE (based on preferred term) is reported for the same subject more than once, the AE is counted only once for that preferred term and at the highest severity and strongest relationship to treatment.

In addition, all AEs (including non-TEAEs), serious TEAEs, TEAEs leading to discontinuation of treatment, and TEAEs leading to dose interruption of treatment will be provided in listings, study site, subject, verbatim term, MedDRA system organ class and preferred term, start and end date, seriousness, severity, relationship to the treatment, action taken with treatment and outcome.

Immune response adverse events due to a severe immune response determined by the Investigator to be possibly, probably or definitely related to B-VEC will be summarized by the number and percentage reporting such AEs along with a subject listing.

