
Statistical Analyses (continued)
	
Efficacy Analyses: The study has a complete randomized-block design in which each subject serves as a block to receive all of the treatment conditions. In this study, each subject provides one pair of matched target wounds with one wound being treated with B-VEC and the other wound with placebo in the primary wound pair. Efficacy measurements are taken multiple times (or repeatedly) over the on-treatment period from each subject. Efficacy measures collected pre-dosing at Visit 1 (Week 1) will be considered as the baseline measurement in this study.
 
Analysis of Primary Efficacy Endpoint: The primary endpoint of the proportion of DEB primary wound sites with complete wound healing of the exact wound surface area selected at baseline will be analyzed using the McNemar Test. The primary endpoint is defined as wounds that meet any of the following conditions:
 
 
• Healed on Week 22 and Week 24, or
 
• Healed on Week 24 and Week 26.
 
 
Only wounds that are healed for at least two (2) consecutive weeks are counted as positive responses.
 
Analysis of Key Secondary Efficacy Endpoint: The key secondary endpoint of the proportion of primary wound sites with complete wound healing of the exact wound surface area selected at baseline, will be analyzed using the McNemar Test. The primary endpoint is defined as wounds that meet any of the following conditions:
 
 
• Healed on Week 8 and Week 10, or
 
• Healed on Week 10 and Week 12.
 
 
Only wounds that are healed for at least two (2) consecutive weeks are counted as positive responses.
 
Analysis of Secondary Efficacy Endpoint: The following secondary endpoint will be analyzed using the Analysis of Covariance (ANCOVA) with treatment as the fixed effect and the baseline value as the covariate by the time points.
 
 
1. The mean change from baseline in pain severity VAS score per wound site associated with wound dressing changes at Weeks 22, 24 and 26 for each treated versus placebo for ages 6 and above on the primary wound pair. For ages below 6 years, the FLACC-R scale scores will be used instead VAS scores.
 
 
Safety Analyses: Safety measures include adverse events, physical examinations, vital signs, and clinical laboratory tests. All safety analyses results will be performed using the safety population. A summary of safety results will be presented for each treatment group.

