3.1.1 Study Design Rationale

The primary objective is to determine whether administration of B-VEC in addition to standard of care improves wound healing as compared to placebo in children, adolescents, and adults with Dystrophic Epidermolysis Bullosa (DEB).

The FDA's guidance Gene Therapy for Rare Diseases (July 2018) suggests that an intra-subject control approach, for such rare skin diseases, may be a useful design. Based on our previous experience (completed B-VEC Phase I/II study) and suggestions from the guidance we will continue to use the intra-subject design in the Phase III study. Each subject will serve as their own control; subjects will have two matched wounds (primary wounds). The primary wounds will be randomized such that one wound will receive B-VEC (active treatment) and the other will receive placebo (inactive treatment). The secondary wounds will receive B-VEC (active treatment), not to exceed the Remaining Weekly Dose. Subjects who enrolled under previous protocol versions, where more than one wound pair was selected, the Investigator's determined a single pair, most closely matched in size, followed by location, to be used for efficacy analysis, following the Agency's guidance.

This Phase III protocol is designed to minimize subject burden by limiting blood draws and removing the collection of biopsies. Experience from the phase I/II portion of the B-VEC trial combined with the advice provided in the FDA's guidance Epidermolysis Bullosa: Developing Drugs for Treatment of Cutaneous Manifestations (June 2019) justifies the proposed design. Molecular correction evaluation from all of the subjects from the Phase I/II study have shown full length COL7 expression by Immuno-fluorescence (IF) (staining for both NC1 and NC2 antibodies) and/or anchoring fibrils by Immuno-electron microscopy (IEM). We believe that robust molecular correction has been demonstrated with wound healing hence the proposed Phase III will mainly focus on evaluation of wound healing as the efficacy endpoint.

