6.3 Treatment Compliance and Exposure

Exposure summary by treatment group (primary wounds only) will be presented for the Safety, mITT, and PP populations. The distribution of subjects by the total number of weeks on therapy (0 through 26) will be presented. For the Safety population, the summary of exposure will be based on the actual treatment received.

Treatment compliance is defined as the number of wound treatment doses (active and placebo) actually received divided by the number of doses expected ($\times 100$) over the time period defined by the first and last treatment dose dates. Descriptive statistics for treatment compliance and the number and percentage of

subjects at least 90% compliant will be presented by treatment group (primary wounds only) for the Safety, mITT, and PP populations.

7 Efficacy Analyses

All data will be presented using summary statistics or frequency tables, as appropriate, and will be analyzed for superiority comparisons between B-VEC and placebo treatments. The description of the sample will be done using summary statistics (n, mean, standard deviation, median, and maximum/minimum) for continuous data and using frequency statistics (counts and percentages) for categorical data. Hypothesis testing, unless otherwise indicated, will be performed at the 5% significance level (2-sided). All P-values will be rounded to four decimal places; P-values less than 0.0001 will be presented as '<0.0001' in all tables. Unless specifically stated, all confidence intervals will be two-sided with 95% coverage.

Efficacy measures collected pre-dosing at Screening or Visit 1 (Week 1) will be considered as the baseline measurement in this study.

The Sponsor, or their designee, will analyze the data using SAS® Statistical Analysis System Version 9.4 or higher.

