7.1.3 Handling of Dropouts or Missing Data

The reason of early study treatment / study discontinuation will be identified, and the percentage of these subjects will be summarized by treatment group.

A multiple imputation approach, described in section 7.1.6, will be used to impute missing values.

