¹¹ All medication taken 3 months prior to Screening/Visit 1 through the end of the study will be recorded as well as all applicable procedures and treatments within the last 3 months to Screening/Visit 1.

¹² On days in which both vitals and blood draw occur, attempt vitals prior to the blood draw. Vitals are collected every 5 visits (i.e. Visit 1; 5; 9; 13; 17; 21; 25; SFU/ET). Vitals may be obtained more frequently as determined by the Investigator.

¹³ A urine pregnancy test will be completed on all women of childbearing potential prior to blood collection and drug administration, as determined by the Investigator.

¹⁴ For Subjects with history of genitourinary involvement, including painful urination due to the underlying disease and or Subjects who are 4 years of age and younger, are not required to provide a urine sample, as determined by the Investigator. Documentation must be recorded on the CRF and listed in Medical History.

¹⁵ Labs will be attempted, unless per the discretion of the Investigator, it is not in the best interest of the subject. If labs are attempted and not obtained, documentation will be noted in the study visit. Furthermore, if labs are not attempted, justification must be recorded in the study visit. The Investigator must determine clinical significance for out-of-range values.

¹⁶ Conduct all other study visit procedures prior to B-VEC and placebo administration. Matched Wounds: IP will be applied to wounds that are open. If a matched wound and neighboring wound is closed, no IP will be applied and application will be reinitiated once the wound reopens at a scheduled visit, as determined by the Investigator. Secondary Wounds: IP will only be applied to open wounds as determined by the Investigator, not to exceed the Remaining Weekly Dose. IP may be applied to immediate neighboring wounds. Up to four (4) unmatched Secondary Wounds may be selected to receive open-label B-VEC during the study treatment. Trace the area that is receiving treatment (including the neighboring wounds). Neighboring wounds are defined as wounds approximately 2-3cm away from the original matched and unmatched (Primary and Secondary) wound.

¹⁷ At the Safety Follow-up (30 days ± 4 days) following the last dose of B-VEC, subjects may roll over into an OLE protocol or will be asked to roll over into a LTFU protocol

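### Subject-level safety tables use treatment groups that do not exist in a within-subject design, the SAP drops the protocol's wound-level adverse event contrast, and no exposure summary covers B-VEC on Secondary Wounds

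*SAP*

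**What the plan says.** Allocation is within the subject. SAP 3.1.1 assigns one primary wound to B-VEC and the other to placebo, and SAP 4.1.2 defines the Safety population as a single set of subjects. B-VEC is also allowed outside the pair. SAP Appendix 1 states: "Up to four (4) unmatched Secondary Wounds may be selected to receive open-label B-VEC during the study treatment".

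Group wording is nevertheless applied to subject-level data in three places:

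- SAP 8.1: incidence by preferred term is "sorted by decreasing frequency in the B-VEC group". The sentence covers all, related and serious TEAEs, and those leading to discontinuation.
- SAP 7.1.3: for early discontinuations, "the percentage of these subjects will be summarized by treatment group".
- Protocol Synopsis, under both the assessments and the safety analyses: "A summary of safety results will be presented for each treatment group".

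On local events, Protocol 8.8 plans the incidence of target-wound adverse events by treatment for each wound pair. Protocol 6.5.1 asks for wound-specific recording where possible. In SAP 8.1 the wound-site-reaction table is by preferred term and severity only. The listing fields it names include no wound, and in all TEAE analyses a repeated preferred term counts once per subject.

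On exposure, SAP 6.3 states: "Exposure summary by treatment group (primary wounds only) will be presented for the Safety, mITT, and PP populations". The metric is time: "The distribution of subjects by the total number of weeks on therapy (0 through 26) will be presented". Compliance has the same scope, with subjects "at least 90% compliant will be presented by treatment group (primary wounds only) for the Safety, mITT, and PP populations". For wounds outside the primary pair, SAP 7.5 plans a listing of healing data and nothing on dose.

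**The concern.** A fever, a laboratory-related event or a withdrawal belongs to a person, and every treated person is meant to receive both products. With no assignment rule, whoever programs the tables must invent one. Either choice yields a B-VEC versus placebo layout that suggests a comparison the trial cannot make.

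The comparison the trial can make is between two randomised wounds in the same person. It is the only randomised safety contrast available, and the SAP does not carry it over from the protocol.

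The exposure gap affects how the event rates are read. Systemic safety reflects all the B-VEC a subject receives. A summary confined to the primary wound, in weeks, does not tell the reader how much that was.

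**Working it through.** **1. Group wording against the unit of randomisation.** Each randomised subject contributes one B-VEC wound and one placebo wound. The set of subjects allocated B-VEC and the set allocated placebo are therefore the same set. A wound-level quantity, such as weeks of treatment of a primary wound, can be split by treatment. A subject-level quantity, such as a systemic event or a withdrawal, cannot. Neither document gives a rule for assigning one.

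**2. The counting rule and local events.** Take one preferred term for a wound-site reaction in one subject:

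| Where it occurs | SAP 8.1 count | Within-pair table (Protocol 8.8): B-VEC / placebo |
|---|---|---|
| B-VEC wound only | 1 | 1 / 0 |
| Placebo wound only | 1 | 0 / 1 |
| Both wounds | 1 | 1 / 1 |

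The SAP table returns the same result for three patterns that mean different things.

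**3. B-VEC outside the primary wound.** The inputs are the unit dose by wound area (4×10^8, 8×10^8 or 1.2×10^9 PFU; SAP Table 1), the Maximum Weekly Dose by age (1.6, 2.4 or 3.2×10^9 PFU; SAP Table 2), and at most four Secondary Wounds within the Remaining Weekly Dose (SAP 2.2.1).

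Remaining Weekly Dose = Maximum Weekly Dose − primary B-VEC unit dose. The plan's own examples reproduce, in units of 10^9 PFU:

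- 3.2 − 0.4 = 2.8 (SAP 2.2.1, age 7)
- 2.4 − 0.4 = 2.0 (Protocol 2.2.1, age 4)
- 1.6 − 0.8 = 0.8 (Protocol 5.1, age 12 months)

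Share outside the primary wound = secondary dose / (secondary dose + primary B-VEC dose). For the three examples with the allowance fully used: 2.8/3.2 = 87.5%, 2.0/2.4 = 83.3%, 0.8/1.6 = 50%. Four wounds can use the whole 2.8, for example 1.2 + 0.8 + 0.4 + 0.4.

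Enumerating zero to four Secondary Wounds of any of the three unit doses under each cap gives the largest possible share:

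| Age | Primary <20 cm² | 20 to 40 cm² | 40 to 60 cm² |
|---|---|---|---|
| ≥6 years | 87.5% | 75% | 62.5% |
| 3 to <6 years | 83.3% | 66.7% | 50% |
| <3 years | 75% | 50% | 25% |

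The maximum exceeds half in 6 of the 9 cells, equals half in 2 and is below half in 1. The minimum is 0% in every cell, because Secondary Wounds are optional.

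Protocol 5.1.1 says 80% of RDEB wounds are 20 cm² or smaller, so small wounds are a natural case. With a primary wound under 20 cm² and k Secondary Wounds of the same class, the share is 4k/(4k + 4):

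- k = 0: 0%
- k = 1: 50%
- k = 2: 66.7%
- k = 3: 75%
- k = 4: 80% (above the cap for subjects under 3 years)

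**The case against.** The best defence is that the group wording is thin. Apart from one sorting phrase, the tables in SAP 8.1 count subjects in a single Safety population and name no group. The same holds for vital signs (SAP 8.2) and laboratory values (SAP 8.4). The explicit sentence sits in the protocol synopsis, and Protocol 8.8 does not repeat it. SAP 9.3 already drops the split by treatment that Protocol 8.8 gives for medications. All of this stands, so it would be wrong to say that the safety tables in general are planned by group. However, the sorting phrase governs the main preferred-term tables and SAP 7.1.3 is explicit.

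It is also fair that the by-treatment exposure table for primary wounds is well defined at wound level, that the protocol already plans the local contrast, and that SAP 5.1 promises listings of all eCRF data, which may include a wound field. A listing is not a summary, though, and the SAP tables as specified do not deliver the contrast.

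A reader might go further in three ways that the documents do not support:

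- That most B-VEC exposure is left out, or that the exposure table shows only 12.5% of it. Secondary Wounds are optional, the share starts at 0%, and the table counts weeks and shows no dose at all.
- That systemic rates will come out equal in both columns. No text puts each subject's events in both columns; the text simply does not say.
- That events under open-label dosing are lost. All adverse events of treated subjects enter the Safety population. What is missing is the summary of the exposure behind them.

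**Conclusion.** The point holds in three parts. Treatment group is undefined for systemic events and discontinuations. SAP 8.1 omits the within-pair summary of target-wound events, and its counting rule merges the two wounds. No exposure or compliance summary covers B-VEC on Secondary Wounds, which can be 0% to 87.5% of a subject's weekly B-VEC.

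The range assumes the current wound caps and a week in which the B-VEC primary wound is dosed at its unit dose. Where a subject falls depends on age, wound size and number of Secondary Wounds, and the documents do not give that distribution. Subjects from earlier protocol versions, who may have further pairs or more than four Secondary Wounds (Protocol 4.1.2.1), are outside the calculation.

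The missing systemic placebo contrast comes from the within-subject design. No table layout can create it, but the plan should not imply that it exists. The primary efficacy analysis is not affected.

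**What to change.** 1. Report subject-level adverse events and discontinuations in one all-subjects column. Remove the group wording from SAP 8.1, SAP 7.1.3 and both places in the protocol synopsis.
2. Restore in SAP 8.1 the summary of target-wound adverse events by wound treatment: primary B-VEC and primary placebo, with secondary B-VEC shown separately where the wound is recorded. Count once per wound, not once per subject, for this table. Add a wound identifier to the adverse event listing.
3. Keep the primary-wound table in SAP 6.3. Add a Safety-population summary of total B-VEC per subject over primary and Secondary Wounds: weeks treated, number of wounds, and PFU derived from the unit dose by wound area.

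The cost is SAP and table-shell wording plus a few extra tables, on data the trial largely records. There are two limits. Wound attribution exists only where it was recorded, since Protocol 6.5.1 asks for it where possible. The documents also do not show whether PFU applied to each Secondary Wound is an eCRF field, so it may have to be derived. No dosing or clinical rule changes.

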### 1.2.2 Safety Results

In every phase of the study, the safety of B-VEC was assessed through analysis of AEs, including clinically significant changes in laboratory results, vitals, and physical exam findings. In addition, viral shedding was analyzed through the collection of serum, urine, and skin swabs, and antibodies to HSV and COL7 were analyzed through collection of blood.

There were no deaths, serious adverse events or significant adverse events reported. Thirty (30) AEs were reported; twenty-nine (29) were mild in severity and one (1) was moderate in severity. The moderate AE was facial itching and redness and unrelated to the Investigational Product. All of the AEs resolved during the study and of the thirty (30), fifteen (15) were unlikely or unrelated, and fifteen (15) were possibly or probably related. Of the fifteen (15) possibly or probably related, four (4) were associated with topical B-VEC administration including rash, fever, itching and peculiar taste.

There were no clinically meaningful changes in laboratory parameters, including liver enzymes. Changes from baseline were small (usually less than 10%) and showed no distinct shifts over time.

Sera samples, collected pre-dose and during specific visits per the Schedule of Events, were evaluated for Anti-Drug Antibodies against HSV and COL7 using a qualified Plaque Reduction Neutralization Test (PRNT). Existing antibodies, as well as any changes in antibodies detected after B-VEC treatment, did not have any apparent impact on subject safety as any possibly related AEs were mild in severity and transient. Efficacy was also not impacted, as evidenced by the robust efficacy of the vector (e.g., indicated by improved wound healing, as compared to intra-subject placebo controls; the observed molecular correction of the collagen VII defect, demonstrated by linear collagen VII deposition and formation of anchoring fibrils along the Basement Membrane Zone (BMZ) by Immunofluorescence (IF) and Immunoelectron Microscopy (IEM).

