A change in the value of a safety laboratory evaluation can represent an AE if the change is clinically relevant (as determined by the Investigator) or if, during treatment with B-VEC, a shift of a parameter is observed from a normal value to a pathological value, or a further worsening of an already pathological value. When evaluating such changes, the extent of deviation from the reference range, the duration until return to the reference range, either while continuing treatment or after the end of treatment with B-VEC, and the range of variation of the respective parameter within its reference range, should be taken into consideration. The Investigator should decide, based on the above criteria and the clinical condition of a subject, whether a change in a laboratory parameter represents an AE. For pathological laboratory values that were not present at baseline, follow-up laboratory evaluations should be performed until the values return to within reference range or until a plausible explanation is found.

AEs should be recorded after the initial IP application through SFU/ET. AEs are to be recorded on the appropriate AE pages in the CRF and in source documents. Where possible, all AEs should be followed to resolution, or an outcome is reached.

Medical tests and examinations are performed, as appropriate, to document resolution of event(s). Where applicable and/or possible, AEs should be recorded as target wound specific.

Adverse events will be graded according to the National Cancer Institute's (NCI's) Common Terminology Criteria for Adverse Events (CTCAE) version 5.0 as applicable.

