### **8.8 Safety Analyses**

The safety and tolerability of B-VEC based on the assessment of adverse events, physical examinations, vital signs, and clinical laboratory test results. All safety analysis results will be performed using the safety population.

Adverse events will be coded using the version of MedDRA System Organ Class and Preferred Term available at the start of the trial. Adverse events will be grouped into treatment-emergent adverse events and post-treatment adverse events and will be tabulated by preferred terminology and by body system. Each AE will be counted once for each subject unless it resolves and recurs, in which case it may appear as multiple AEs. Severity, frequency, and relationship of AEs to study intervention will be presented by System Organ Class (SOC) and preferred term. Incidence of target-wound-related adverse events will be summarized by treatment, respectively, for each wound pair.

Listings will be provided for discontinuations, deviations, compliance, AEs leading to discontinuation, and target-wound-related adverse events. AE listings will include severity and relationship to study medication, as well as actions taken.

Tables will be provided summarizing reasons for premature discontinuation, protocol deviations, subject compliance, treatment-emergent AEs (TEAEs), TEAEs of target wound, TEAEs by severity, SAEs, and TEAEs leading to discontinuation.

The prior and concomitant medications will be summarized and listed by treatment. Medications will be coded with WHO Drug and categorized as either prior medications (any medication that was started before the first application of B-VEC) or concomitant medications (medication continued or newly started on or after the date of first application of B-VEC).

Medical/procedural history data collected during Screening or Visit 1 (Week 1), will be summarized by MedDRA System Organ Class and Preferred Term.

Descriptive summary of physical examinations, vital signs, and clinical laboratory tests will be reported along with data listings.

Evaluations of viral shedding, infectivity, COL7 and HSV antibodies will be done descriptively.

Any abnormal lab tests obtained during the study will be listed for individual subjects. Any positive findings of the pregnancy test will be listed.

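### SAP 8.1 does not carry forward the protocol's target-wound adverse event outputs, so the randomised within-pair comparison of adverse events is not produced

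*SAP*

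**What the plan says.** The protocol sets up wound-level recording and then plans to use it. Section 6.5.1 tells sites: "Where applicable and/or possible, AEs should be recorded as target wound specific". Section 8.8 plans three outputs on that basis:

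- A comparison within the pair: "Incidence of target-wound-related adverse events will be summarized by treatment, respectively, for each wound pair".
- A table, named in the list "treatment-emergent AEs (TEAEs), TEAEs of target wound, TEAEs by severity, SAEs, and TEAEs leading to discontinuation".
- A listing, named at the end of the list that includes "AEs leading to discontinuation, and target-wound-related adverse events".

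SAP 8.1 sets out the adverse event displays in detail. Its only display of local events is this one, broken down by preferred term and severity: "The number and percentage of subjects reporting a TEAE of wound site reaction (based on the MedDRA higher level term) will be tabulated". The event listings in the same section are to show "study site, subject, verbatim term, MedDRA system organ class and preferred term, start and end date, seriousness, severity, relationship to the treatment", followed by action taken and outcome. Neither the table nor these variables refer to P1, P2, a Secondary Wound or a target wound.

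**The concern.** A MedDRA term says what an event was. It does not say at which wound it occurred. In this trial the wound determines the treatment: one primary wound receives B-VEC, the other receives placebo gel, and up to four Secondary Wounds receive open-label B-VEC in the same person. A display chosen by term alone can therefore mix events from wounds on different treatments with events at untreated wounds. It can also miss events at a primary wound that were coded under another term.

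At stake is the adverse event comparison that randomisation within the pair makes possible. Every treated subject is planned to receive both products, so a table that counts subjects has no placebo group to set beside a B-VEC group. A statement on how B-VEC compares with placebo gel for local adverse events needs wound-level counts.

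**Working it through.** The documents give no figure to reproduce, and the point rests on no sample size, alpha or event rate. The check is a comparison of text.

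**Step 1. Match each protocol output to the SAP.**

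| Planned in Protocol 8.8 | In SAP 8.1 |
|---|---|
| Incidence of target-wound events by treatment, within the wound pair | Not named |
| Table of TEAEs of the target wound | Not named; the nearest is the wound site reaction table, selected by MedDRA higher level term |
| Listing of target-wound events | Not named; the listing variables include no wound identifier |

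All three of the three outputs are absent.

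**Step 2. Look for a substitute elsewhere in SAP section 8.** The other displays in 8.1 count subjects: the overall summary, then tables by system organ class and preferred term, severity, relationship, seriousness, discontinuation and dose interruption, and a summary of severe related immune responses. One table is to be sorted by frequency in a B-VEC group, but 8.1 does not define such a group for subjects who each have both treatments. Under 8.3, physical and skin examination results are listed by body system. None of these gives a comparison between P1 and P2.

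**Step 3. Check whether the wound site reaction table is restricted to the primary pair.** No sentence restricts it or splits it by wound treatment. The SAP does make this restriction elsewhere: section 6.3 presents exposure and compliance by treatment group for primary wounds only. The restriction would therefore have to be written into 8.1 to apply there.

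**Step 4. Follow what enters the table.**

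- An event within the term at P1, P2, a Secondary Wound or an untreated wound is counted, with nothing to tell these apart.
- An event at P1 or P2 coded outside the term is not counted. The protocol foresees wound infection (6.4.2) and allergic reaction or malignancy at a treatment site (6.11). Whether these fall under the term depends on the MedDRA hierarchy, which the documents do not reproduce, so the number missed cannot be calculated.
- Events missed here that are TEAEs still enter the general tables, without wound attribution.

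**Step 5. Check that the data could exist.** Protocol 6.5.1 asks for wound-specific recording, qualified by applicability and feasibility, and the outputs in 8.8 presuppose it. Neither document describes the eCRF item or says that it identifies P1, P2 and S1 to S4 individually. Attribution may therefore be incomplete.

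**The case against.** The strongest reply is that nothing has been contradicted. The wound site reaction table is an ordinary subject-level display, and the SAP never calls it the within-pair comparison or a replacement for Protocol 8.8. The protocol says the SAP adds detail, so its own outputs remain in force. Events are not lost either: TEAEs are tabulated, all AEs are listed with their verbatim term, and SAP 5.1 promises listings of all eCRF data, which would include wound attribution if it is an eCRF item. No test depends on any of this.

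Much of that stands. The MedDRA-term table is legitimate and should be kept, and the listing gap is softened by SAP 5.1. What remains is that 8.1 specifies the adverse event tables in detail and omits the wound-level ones. Outputs produced from the SAP as written would contain no comparison of adverse events between B-VEC and placebo wounds.

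Three stronger readings are tempting, and the documents do not support them.

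- *None of the four Phase I/II event types would be captured.* Protocol 1.2.2 says "four (4) were associated with topical B-VEC administration including rash, fever, itching and peculiar taste". Fever and peculiar taste are not local events, the sentence does not place the rash or itching at a wound, and the preferred terms under the higher level term are not shown.
- *Up to two thirds of the events in the table would come from outside the pair, because four of six study wounds can be Secondary Wounds.* That counts wounds, not events. It needs equal risk per wound, which is stated nowhere, and the full number of Secondary Wounds, which the Remaining Weekly Dose limits. In the example in Protocol 5.1, the remaining dose covers one Secondary Wound of 20 to 40 cm².
- *This is the only randomised, blinded safety comparison.* Viral shedding and infectivity swabs are also taken from both primary wounds (Schedule of Events, footnote 8).

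**Conclusion.** The point holds as a gap between protocol and SAP with a real consequence. Three planned target-wound outputs are missing from SAP 8.1, and the one local table there cannot separate events at the B-VEC primary wound, the placebo primary wound, Secondary Wounds and untreated wounds. Under the SAP as written, the randomised within-pair comparison of adverse events is not produced.

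Its size is limited. It concerns descriptive safety reporting and leaves the primary and key secondary analyses untouched. No count of missed or misplaced events can be given.

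The conclusion rests on two assumptions: that the safety tables are programmed from SAP 8.1, and that target wound in Protocol 8.8 means the primary pair. Protocol 8.8 supports the second by tying the term to the wound pair, but Protocol 6.2.1.2 uses target wounds when introducing an assessment of both Primary and Secondary Wounds, so the SAP should settle the meaning. The change should be made before unblinding.

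**What to change.** In SAP 8.1:

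1. Add a table of TEAEs recorded as specific to P1 or P2, with any preferred term, by preferred term and severity, in paired columns for the B-VEC wound and the placebo wound. Show events specific to Secondary Wounds separately where recorded.
2. Add a wound identifier to the adverse event listing, and name the target-wound listing from Protocol 8.8.
3. State that target wound in this table means the Primary Wound Pair. Say also where events at additional randomised pairs are shown for subjects enrolled under earlier protocol versions.
4. Keep the MedDRA-term table as a supplementary display.
5. Report the number of TEAEs with no recorded wound.

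The cost is SAP wording, one table shell and one listing variable, provided that sites recorded attribution as Protocol 6.5.1 asks. If the eCRF holds only a general target-wound flag, assigning events to P1, P2 or a Secondary Wound would need blinded queries to sites. The downside is that events without a recorded wound would appear only in the subject-level tables, which is why their number should be reported.
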